7.9.4 Determination of Subjects/Data for Analysis

Enrolled subjects who have Reveal LINQ™ device successfully inserted and have the LINQ™ HF investigational RAMware successfully downloaded to the device and who have completed a first successful CareLink transmission.

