### 12.1 Adverse Events

To ensure that all AEs that are potentially relevant are collected, the following subset of AEs will be collected throughout a subject's participation, starting at the time the informed consent form is signed:

- All Reveal LINQ™ Procedure related AEs
- All Reveal LINQ™ System related AEs
- All Serious AEs
- All Pulmonary related AEs
- All Cardiovascular related AEs

Reporting of AEs to Medtronic will occur on an Adverse Event e-CRF, including a description of the event, the diagnosis, the date of event onset, the date the site became aware of the event, the relatedness and seriousness of the event, diagnostic tests and procedures performed, actions taken as a

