7.1.3 Analysis Sets

Enrolled subjects who have Reveal LINQ™ device successfully inserted, the LINQ™ HF investigational RAMware successfully downloaded to the device and have completed a first successful CareLink transmission will be included in the analysis of the primary objective.

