7.9.3 Analysis Methods

Data from multiple study components will be collected in this study, of which the Reveal LINQ™ HF derived data is of the most interest. This includes subcutaneous electrocardiogram, impedance, temperature, accelerometer and patient activity measurements.

Descriptive statistics such as mean and standard deviation for continuous variables and count and proportion for categorical variables will be used to summarize the derived data from Reveal LINQ™ HF. The relationship between changes in LINQ™ derived data and COPD events per EAC adjudication will be evaluated. Specifically, for each subject that has experienced at least one COPD event per EAC adjudication, the average daily measurements of LINQ™ derived data before and after a COPD event will be plotted to identify patterns and signals related to the occurrence of the COPD event.

In addition, exploratory survival analyses for time to first COPD event through 12-months of follow-up such as a Kaplan-Meier curve and Cox proportional hazards regression models with independent variables such as demographics and comorbidities will be included.

Each subject's time to first detected and adjudicated COPD event will be defined as the time from insertion date to the onset date of first COPD event. Subjects who have not experienced a COPD event through 12 months will be censored at:

- (1) their point of last contact, usable Reveal LINQ ICM interrogation or CareLink transmission if they occur before or at 12 months, whichever is later

or

- (2) 12 months (374 days) if their point of last contact, usable Reveal LINQ ICM interrogation or CareLink transmission go beyond 12 months.

Survival estimates and hazard rate with 95% confidence intervals will be reported.

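### The exploratory time-to-first-COPD-event analysis starts at insertion but drops inserted subjects who never transmit, together with any COPD events they had

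*SAP*

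**What the plan says.** SAP 7.9.3 adds "exploratory survival analyses for time to first COPD event through 12-months of follow-up" to the descriptive sensor work: a Kaplan-Meier curve and Cox models, with demographics and comorbidities as example covariates. Each subject's time is "defined as the time from insertion date to the onset date of first COPD event". Event-free subjects are censored at the latest of three sources, "their point of last contact, usable Reveal LINQ ICM interrogation or CareLink transmission if they occur before or at 12 months", or at "12 months (374 days) if their point of last contact" or either device source runs later.

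The selection rule follows directly in SAP 7.9.4: successful insertion, successful RAMware download, "and who have completed a first successful CareLink transmission". SAP 7.1.3 gives the same set and says that subjects who "have completed a first successful CareLink transmission will be included in the analysis of the primary objective". Protocol 14.3.4 has the same transmission condition. No deadline for the first transmission, landmark, delayed entry or separate set for the survival analyses appears in either document.

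COPD events come from another source. SAP 7.9.2 uses adverse events adjudicated by the Event Adjudication Committee (EAC), and Protocol 12.1 says that "the following subset of AEs will be collected throughout a subject's participation, starting at the time the informed consent form is signed"; pulmonary events are in that subset. Protocol 10.23.1 adds that a subject's data up to exit will be used for analysis.

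**The concern.** A subject enters the risk set at insertion only if something happens later. A subject who is inserted, has a COPD event and dies or withdraws before ever transmitting is absent from both numerator and denominator. So is one who stays in the study but never gets the monitor working. If these subjects differ in risk from the rest, the curve describes transmitters rather than inserted subjects. Cox coefficients may also be distorted for covariates linked both to not transmitting and to events, such as age or comorbidity burden.

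The before/after sensor plots cannot be made without device data, so the restriction is natural there. The survival analysis is different. Its outcome is an adjudicated adverse event, its named covariates are baseline characteristics, and its censoring rule accepts last contact. Time at risk and event status can both be established for a non-transmitter. The restriction therefore discards usable subjects from a cohort of at most 100.

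**Working it through.** **The plan's own figure (SAP section 6).** 60 subjects × 2 exacerbations per year × 1 year = 120; × 50% meeting the definition = 60 COPD events. This reproduces, and implies 60 / 60 = 1 COPD event per patient-year.

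**Who is lost and who stays, reading 7.9.3 with 7.9.4**

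| Inserted subject | In the set? |
|---|---|
| COPD event first, first transmission later | Yes, with the event |
| Transmits once, then dies or exits | Yes, counted or censored |
| Dies or exits before any transmission | No; any event is lost |
| Stays in the study but never transmits | No; any event is lost |

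Only the last two rows, the never-transmitters, are affected by the transmission condition.

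**Assumptions.** The documents give no non-transmission rate. Let a share f of inserted subjects never transmit, with event rate r times that of transmitters. Take f = 2 to 10% and r = 1.5 to 3, with a constant hazard of 1 per year in transmitters. At the SAP's 374-day horizon, transmitters have F = 1 − exp(−374/365) = 0.641.

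**Case A: never-transmitters stay under follow-up all year.** The full-cohort value is (1 − f)F + fF(r), with F(r) = 1 − exp(−r × 374/365). The difference from the transmitter-only curve is f × [F(r) − F].

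- F(1.5) = 0.785; F(3) = 0.954; F(0.5) = 0.401.
- f = 2%: 0.29 points (r = 1.5) to 0.63 points (r = 3).
- f = 10%: 1.44 points (r = 1.5) to 3.13 points (r = 3).
- r = 1: zero, although the events are still discarded.
- r = 0.5: −0.48 points (f = 2%) to −2.40 points (f = 10%), so incidence is overstated.
- First events lost per 60 subjects, 60 × f × F(r): from 60 × 0.02 × 0.785 = 0.9 to 60 × 0.10 × 0.954 = 5.7.
- Stretching f to 20% with r = 3 gives 0.20 × 0.313 = 6.3 points.

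**Case B: never-transmitters exit early.** Let exit be uniform over the first D days. A full-cohort Kaplan-Meier would censor these subjects at exit, so each contributes only D/2 days on average. The added cumulative hazard is approximately f × (r − 1) × (D/2)/365. Multiplying by the 374-day survival, 1 − 0.641 = 0.359, gives the change in incidence.

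- D = 14, f = 2%, r = 1.5: 0.02 × 0.5 × 7/365 × 0.359 = 0.01 points.
- D = 14, f = 10%, r = 3: 0.10 × 2 × 7/365 × 0.359 = 0.14 points.
- D = 32, f = 2%, r = 1.5: 0.02 × 0.5 × 16/365 × 0.359 = 0.02 points.
- D = 32, f = 10%, r = 3: 0.10 × 2 × 16/365 × 0.359 = 0.31 points, also 0.31 by numerical integration of the mixed hazard.
- Events lost per 60 subjects in this last case: at most about 6 × 3 × 16/365 = 0.8, fewer than one.

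The 14 and 32 days are the manual-transmission interval and the overwrite limit in Protocol 10.11.

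**The case against.** **Scope.** SAP 7.1.3 ties the set to the primary objective, and the survival analyses are an exploratory addition that the protocol does not contain. No sentence applies 7.9.4 to them. That is so, but they sit in 7.9.3 directly above 7.9.4, under the same objective, and no other set is defined. If 7.9.4 does not govern them, their population is unstated and the same sentence is needed.

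**Mitigation.** The STROBE diagram (SAP 7.1.1) shows deaths and exits. Baseline tables (7.6) cover all enrolled subjects as well as the analysed subset, and the adverse event listing (7.10) gives days from insertion. Protocol 10.11 and 10.12.1 provide missed-transmission reports and reminders, which make a full year without any transmission unlikely. These measures reveal or limit the exclusions; they do not correct the estimates.

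**Stronger readings that the documents do not support**

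- *Guaranteed event-free time before the first transmission.* Being alive and in the study is guaranteed; being free of COPD events is not. An event on day 5 followed by a first transmission on day 10 is kept.
- *All early deaths and exits are lost.* Only those before a first transmission are.
- *The loss is 3.8% or 8.4% of subjects.* Those are the shares with a first event within 14 or 32 days, 1 − exp(−14/365) and 1 − exp(−32/365). Nothing says that these subjects never transmit. Protocol 10.11 also provides automatic nightly transmission. If that counts as the first, the gap may be about a day, in which 0.3% have an event.
- *The bias has one direction.* That follows only from assuming r above 1. Poorly engaged subjects may report fewer events.
- *The analysis uses no LINQ data.* Interrogations and transmissions are permitted censoring sources, the covariate list is open, and Protocol 10.10 has device data reviewed alongside diary and CRF data to track potential events. The supportable claim is narrower: a transmission is not required.

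A common cohort for the plots and the survival curve is also a defensible presentational choice, and the analysis has no hypothesis. Both points bear on priority, not on whether the selection exists.

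**Conclusion.** The structural point stands. Entry to a risk set that starts at insertion depends on a later transmission, and inserted subjects who never transmit are removed with any COPD events. Dropping subjects who exit before transmitting also sits badly with the rule in Protocol 10.23.1 that data up to exit are used.

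The effect is of unknown size and probably small. With 2 to 10% never transmitting at 1.5 to 3 times the event rate, the understatement is about 0.01 to 0.3 points if they leave within 14 to 32 days. It reaches 0.3 to 3.1 points, against 64.1%, only if they are followed all year without one transmission. These figures rest on a constant hazard and on assumed f and r. Lower event rates in non-transmitters would reverse the sign. The distortion of Cox coefficients cannot be quantified from the documents.

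No hypothesis, power or error rate is affected, so this is a desirable improvement rather than an essential one.

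**What to change.** In SAP 7.9.4, limit the RAMware-download and transmission conditions to the LINQ data summaries and the before/after event plots. State that the exploratory Kaplan-Meier and Cox analyses include every subject with a successful insertion, from the insertion date, whether or not they transmitted. Keep the existing 374-day limit and let last contact serve as the censoring date where there is no usable interrogation or transmission. Align 7.1.3 with this, and report the number of inserted non-transmitters and their adjudicated COPD events beside the curve.

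The adverse event and contact data are already being collected, so the cost is a sentence of text and a second analysis set to define and label. Event capture may be somewhat less complete in subjects without device data, which the report can note.

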7.10 Safety Evaluation

All adverse events that are Reveal LINQ™ system-related or procedure-related are reported with onset occurring between a subject's consent and exit will be summarized. An overall summary table will be generated that shows the number of events and number and percentage of subjects that experience adverse events for each category of seriousness, complication/observation status, whether the event is an Unanticipated Adverse Device Effect (UADE), and each level of relatedness to the procedure and/or Reveal LINQ™ system.

Adverse events will each be assigned a Medical Dictionary for Regulatory Activities (MedDRA) term and will be summarized by MedDRA preferred term. The statistics will include the number of adverse events assigned that term, the corresponding number and percentage of subjects who experienced such an adverse event. Separate tables will be done in this way for all adverse events, for just the procedure-related adverse events, and the Reveal LINQ™ system-related adverse events.

A listing table of all adverse events will also be generated. Each row will contain the subject ID, the MedDRA preferred term, the onset date and days post-insertion, whether the event was a complication or observation, whether the event was serious, the relatedness to the procedure or system (if any), a summary of actions taken in response to the event, and the outcome of the event (whether it was resolved, and the date of resolution).

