## 6.1 Duration

Subjects will be followed until the last enrolled subject reaches their 6-month visit or until official study closure defined as when Medtronic and/or regulatory requirements have been satisfied per the Clinical Investigation Plan (CIP) and/or by a decision by Medtronic or the applicable external parties (i.e. Ethics Committee (EC) Regulatory Authority) whichever occurs first. The estimated total study duration is approximately 33 months, representing a 26-month enrollment period, at least 6 months of follow-up per subject and up to 1 month between enrollment and insertion.

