## 14. Statistical Design and Methods

The LINQ™ for COPD is a prospective, non-randomized, multi-center, observational, pre-market clinical study. The purpose of the study is to characterize the Reveal LINQ™ derived data from patients with COPD.

This is a feasibility study that is exploratory in nature and with no hypothesis. Therefore, justification on sample size is not required. The study plans to enroll up to 100 subjects from up to 10 centers in the United States, with no more than 20 subjects enrolled per site. Enrolled subjects are expected to be followed up for at least 12 months after the insertion of Reveal LINQ™ device and download of either the LINQ HF or ALLEViate-HF investigational RAMware. The expected total study duration is approximately 33 months, representing approximately 26 months of patient enrollment and 6 months of subject follow-up with up to 1 month between enrollment and insertion.

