4.1 Primary Objective

The primary objective is to characterize Reveal LINQ™ derived data from patients with COPD by assessing the relationship between changes in LINQ™ derived data with subsequent COPD events.

COPD event is defined as an adverse event where the underlying COPD condition exacerbates beyond normal day-to-day variations, where an increase in dyspnea, cough, and/or sputum production presents with acute onset and necessitates supplementing regular COPD medications with antibiotics for respiratory pathogens and/or steroids.

5. Investigation Plan

The LINQ™ for COPD is a prospective, non-randomized, multi-center, observational, pre-market clinical study. The study may enroll up to 100 COPD subjects at up to 10 sites in the US, with no more than 20 subjects enrolled per site. Study subjects will be followed until the last enrolled subject reaches their 12-month visit or until official study closure defined as when Medtronic and/or regulatory requirements have been satisfied per the Clinical Investigation Plan and/or by a decision by Medtronic or regulatory authority, whichever occurs first. Accordingly, the expected total study duration is approximately 25 months, representing approximately 12 months of patient enrollment and 12 months of subject follow-up with 1 month between enrollment and insertion. All Reveal LINQ™ system and procedure-related adverse events will be collected and reported per the study protocol. In addition, all SAEs, all Respiratory related AEs (regardless of seriousness) and all Cardiovascular related AEs (regardless of seriousness) will be collected and reported per study protocol.

Following consent, subjects will undergo a baseline assessment followed by the LINQ™ ICM device insertion procedure. Following insertion, subjects will complete a daily diary entry, which includes answering the BCSS Questionnaire and recording any PRN medications. Additionally, subjects will complete telephone follow-up visits every three months post device insertion (visits may also be conducted in-person if desired). The 6-month follow-up visit however, will need to be conducted in office. All enrolled subjects will be followed until study closure. A study flowchart is shown in Figure 1.

[figure not shown]

Figure 1: Study Flowchart

The subject population for the LINQ™ for COPD study is COPD patients who are known to have frequent exacerbations (at least two in the past year). Inclusion and Exclusion criteria are listed below.

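### Planned follow-up runs from about 6 to 32 months, so the crude AE percentages in SAP 7.10 have no common time horizon; add person-time and fixed-time estimates, and state the averaging unit for the sensor summaries

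*SAP*

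**What the plan says.** **Follow-up.** Protocol 6.1 sets a common closing date: "Subjects will be followed until the last enrolled subject reaches their 6-month visit or until official study closure". It gives the total duration as "approximately 33 months, representing a 26-month enrollment period, at least 6 months of follow-up per subject and up to 1 month between enrollment and insertion". Protocol 10.23.1 adds that everything collected up to a subject's exit goes into the analysis.

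Two other places differ. Protocol section 14 states: "Enrolled subjects are expected to be followed up for at least 12 months after the insertion of Reveal LINQ™ device". SAP section 5 (Investigation Plan) still has the older design: "approximately 25 months, representing approximately 12 months of patient enrollment and 12 months of subject follow-up with 1 month between enrollment and insertion".

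**Adverse events.** SAP 7.10 counts onsets from consent to exit: "An overall summary table will be generated that shows the number of events and number and percentage of subjects that experience adverse events". The tables by MedDRA term likewise give events, subjects and percentages, for all AEs and separately for procedure-related and system-related AEs. The AE listing shows days since insertion.

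**Sensor data.** SAP 7.9.3 states: "Descriptive statistics such as mean and standard deviation for continuous variables and count and proportion for categorical variables will be used to summarize" the device data. It does not say whether the unit is the day or the subject. The same section plans per-subject plots around each COPD event, and a Kaplan-Meier and Cox analysis of first COPD event censored at 12 months.

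**The concern.** When subjects are observed for very different lengths of time, the percentage with at least one event mixes short and long exposures. It describes neither 6 months, nor 12, nor any other stated time. The same underlying event rate gives a different percentage if enrolment is quicker or slower.

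This matters most where events accumulate. The all-AE tables include serious, pulmonary and cardiovascular events (Protocol 12.1), and Protocol Table 8 recognises that pocket infection can arise while the device stays in place. It matters least for procedure-related events, most of which can be expected soon after insertion.

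The sensor summaries raise a related but smaller question. A COPD event is defined as worsening outside normal daily fluctuation, and Protocol 4.2 looks ahead to a prediction algorithm. The spread needed to judge a pre-event change is the day-to-day spread within a subject. The plan provides no numerical summary of it: an SD over all daily records would combine it with differences between subjects, and an SD over subject means would leave it out.

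**Working it through.** **1. The plan's own figures.** Protocol 6.1: 26 + 6 + 1 = 33 months. SAP section 5: 12 + 12 + 1 = 25 months. Both totals reproduce.

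**2. Range of follow-up after insertion.**

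- Current protocol: the last subject has 6 months. The first has 33 months less up to 1 month before insertion, so 32 to 33. Using 32, the ratio is 32/6 = 5.3.
- SAP text: about 12 to 24 months, ratio 2.

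**3. Assumptions for the illustration (not in the documents).** Insertion is uniform over 26 months, nobody drops out, and each subject has the same constant AE rate r per year. Follow-up is then uniform from a = 6 to b = 32 months, with mean (6 + 32)/2 = 19 months.

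- Risk by month m: 1 − exp(−r·m/12).
- Expected crude percentage: 1 − [exp(−r·a/12) − exp(−r·b/12)] / [r·(b − a)/12].

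Example, r = 0.2: exp(−0.1) = 0.9048 and exp(−0.5333) = 0.5866. The difference is 0.3182, and 0.3182/0.4333 = 0.734, so the crude percentage is 26.6%.

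| AE rate per year | 6 months | 12 months | 32 months | Crude, consent to exit |
|---|---|---|---|---|
| 0.1 | 4.9% | 9.5% | 23.4% | 14.5% |
| 0.2 | 9.5% | 18.1% | 41.3% | 26.6% |
| 0.5 | 22.1% | 39.3% | 73.6% | 52.4% |
| 1.0 | 39.3% | 63.2% | 93.1% | 75.2% |

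The last row uses the plan's own event assumption (Protocol 14.4, SAP section 6): 2 exacerbations per patient-year × 50% meeting the definition = 1 COPD event per patient-year. The other rates are assumed, to show a range.

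**4. Dependence on enrolment speed.** Keep r = 0.2 and the same 6-month closing rule, but let enrolment take 12 months (follow-up 6 to 18 months). The crude percentage falls from 26.6% to 18.0% with no change in the event rate.

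**5. The SAP's 12 to 24 months.** At r = 0.2 the crude percentage is 25.8%, close to 26.6% because mean follow-up is similar (18 against 19 months). The missing horizon is therefore present under either design. The current protocol widens the spread between subjects, and about (32 − 12)/26 = 77% of subjects would reach 12 months instead of all of them.

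**6. Sensor weighting, if daily records were pooled.** The earlier half of enrollees averages (32 + 19)/2 = 25.5 months and the later half (19 + 6)/2 = 12.5 months. The earlier half's share of follow-up days is 25.5/38 = 67%. Under 12 to 24 months it is 21/36 = 58%. If each subject is averaged first, each half counts 50%.

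**The case against.** The strongest reply is that this is a single-arm, exploratory study with no hypothesis. Protocol 6.2 says safety is not its main focus, and Protocol 10.19 makes the AE summary ancillary. No comparison with other LINQ data is planned. The AE listing gives days since insertion for every event in at most 100 subjects. Unequal follow-up is already handled for first COPD event by censoring at 12 months. All of this stands, and it limits the consequence. It does not give the printed percentages a time horizon, and in a descriptive study those percentages are the result.

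Three stronger readings are tempting, but the documents do not support them:

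- **That the AE percentages refer to no defined period.** SAP 7.10 does define one, consent to exit. Its length differs between subjects, which is a narrower fault.
- **That sensor data are pooled so that early enrollees dominate.** SAP 7.9.3 names no averaging unit. The 67% applies only if daily records are pooled, and even then it is two thirds against one half. It also treats every follow-up day as a sensor day, whereas Protocol 10.11 warns of overwriting when manual transmissions are missed.
- **That within-subject variation is never seen.** The event-aligned daily plots display it for subjects with a COPD event. What is missing is a number, and any figure for subjects without an event.

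It is also fair to say that a constant rate is a poor model for procedure-related events. The illustration should not be applied to them; the 30-day estimate is the useful one there.

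**Conclusion.** The point holds for the AE tables, and in a limited form for the sensor summaries. Planned follow-up differs about fivefold under Protocol 6.1, and SAP 7.10 has neither a person-time denominator nor a fixed time point. For assumed rates of 0.1 to 0.5 per year, the crude percentage is about 1.3 to 1.5 times the 12-month risk (52.4/39.3 and 14.5/9.5). That rests on uniform insertion, no dropout, no early closure and a constant rate common to all subjects; real departures would change the figures but would not supply the missing horizon.

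For the sensor data, the conclusion is only that the averaging unit should be stated and the within-subject SD reported. The event-aligned plots and the 12-month COPD-event analysis are largely unaffected. The conflicting statements of minimum follow-up in Protocol 6.1, Protocol section 14 and SAP section 5 need reconciling. Overall this is a cheap improvement and does not threaten the study's main analysis.

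**What to change.** 1. **SAP 7.10.** Add patient-years of follow-up and events per patient-year to each AE table. For system- and procedure-related AEs, add Kaplan-Meier percentages at fixed times, for example 30 days, 6 months and 12 months, counted from insertion as SAP 7.9.3 already does for first COPD event.
2. **SAP 7.9.3.** State that each subject's mean and day-to-day SD are computed first and then summarised across subjects, with between-subject and within-subject SD reported separately.
3. **Follow-up description.** Bring SAP sections 3, 4, 5 and 7.1.1 and Protocol section 14 into agreement with Protocol 6.1, and report the distribution of follow-up actually achieved.

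The cost is some SAP wording and a few extra table columns. The dates needed are already collected, and analysis does not start until all subjects have exited. The only downside is slightly longer tables.
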